	
study single body changes occurring during pregnancy will alter the study results.
 
22. Recent vaccination within the last 2 weeks prior to study baseline visit. Routine or standard of care vaccinations (such as SARS-CoV-2, influenza, pneumococcal, and meningococcal vaccinations) are allowed but must be administered greater than 14 days prior to baseline study visit. For SARS-CoV-2 vaccination, the last dose must be administered at least 14 days prior to baseline study visit.

TEST PRODUCT, DOSE, AND ROUTE OF ADMINISTRATION	
Oral methamphetamine hydrochloride (10 mg, then 15 mg) will be administered in a double-blind fashion and prepared by over-encapsulating commercially available drug with cornstarch.

CONTROL PRODUCT, DOSE AND ROUTE OF ADMINISTRATION	
Placebo capsules will be administered in a double-blind fashion and prepared by over-encapsulating cornstarch.

DURATION OF PARTICIPANT PARTICIPATION AND DURATION OF STUDY	
Participants will be randomized to either of two treatment arms, oral methamphetamine or placebo, using a crossover design with a 31-day washout period in between treatment arms. Participants will be on study for up to 146 days.
 
Screening (for each arm): up to 14 days prior to treatment arm.
 
Treatment (for each arm): 1 day (participants to be admitted to outpatient research unit for a total of 5 hours on the treatment day)
 
Follow-up (for each arm): 31 days after the initial dose for that treatment arm.
 
The total duration of the study is expected to be 146 days (approximately 5 months).

CONCOMMITANT MEDICATIONS	
Prohibited:
 
Strict criteria for potential medications that could interact with the study drug will be used, and the following medications are not allowed during the study because of potential interactions with the study medication: acebropyline, iobenguane, isocarboxazid, methylene blue, moclobemide, phenylzine, procarbazine, rasagiline, safinamide, selegiline, tranylcypromine, asunaprevir, bupropion, topical cocaine, fluoxetine, iohexol, linezolid, paroxetine, potassium citrate, quinidine, sodium bicarbonate, sodium citrate, sodium lactate, tipranavir, and tromethamine. This is because the study medication may alter metabolism of the drugs.
 
Allowed:
 
Otherwise, participants may use their usual medications, as long as they are medically necessary and can be monitored safely during the study period.

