6.2 Inclusion Criteria

2. Willing and able to provide written informed consent
3. Male or female, age ≥ 18 years and ≤ 65 years
4. Laboratory confirmed documentation of HIV-1 infection.
5. Continuous therapy with a DHHS recommended/alternative combination ART for least 12 months (at least 3 agents) at study entry with no regimen changes in the preceding 12 weeks
6. Maintenance of undetectable plasma HIV-1 RNA below the limit of quantification for at least 12 months. Episodes of single HIV plasma RNA 50-500 copies/ml will not exclude participation if subsequent HIV plasma RNA is below the limit of assay detection.
7. No plans to modify ART during the study period (146 days, or approximately 5 months)
8. Participant and partner(s) are willing to use two forms of contraception throughout the study period as well as up to 60 days after the last day of study completion.
9. Ability and availability to participate in the full 146 days of the study (approximately 5 month) and maintain the inclusion/exclusion criteria
10. No current or prior history of methamphetamine (MA) use disorder by DSM-5 diagnostic criteria. Participants may have a prior history of taking prescription

medications containing amphetamines-type stimulants such as Adderall® or Dexedrine® or Ritalin for the treatment of conditions such as attention deficit hyperactivity disorder as long as the participant has not taken these medications in the last 12 months or plans to take these medications during the entire study period.

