6.3 Exclusion Criteria

11. History of methamphetamine (“meth”) use disorder by DSM-5 diagnostic criteria using the 11-symptom checklist.
12. Evidence of MA use other than due to the administered oral methamphetamine study drug, based on urine, hair, or serum MA measurements collected at baseline and follow-up study visits.
13. Current use of prescription medications containing amphetamine-type stimulants (e.g., Adderall®, Dexedrine®, Ritalin, etc.) within the past 1 year.
14. Sensitivity or allergy to amphetamine-type stimulants
15. Current use of any other “psychoactive” drug within the last 1 month. These include cocaine, ecstasy, LSD, mushrooms, or other recreational drugs – but cannabis, nicotine or caffeine use is ok.
16. Use of illicit opioids (heroin, fentanyl) – but ok if use of prescription opioid agonists with known prescribed doses, such as methadone, hydrocodone (Norco®), buprenorphine/naloxone (Suboxone®), oxycodone (Oxycontin®), hydromorphone (Dilaudid®) within the past 3 months by self-report and/or urine qualitative screening.
17. Current moderate to severe use of alcohol use disorder (DSM-5 criteria) as this might put patient at risk of withdrawal during the study.
18. Recent use within the last month of the following medications given potential interactions with oral methamphetamine: acebromphyline, iobenguane, isocarboxazid, methylene blue, moclobemide, phenylzine, procarbazine, rasagiline, safinamide, selegiline, tranylcypromine, asunaprevir, bupropion, topical cocaine, fluoxetine, iohexol, linezolid, paroxetine, potassium citrate, quinidine, sodium bicarbonate, sodium citrate, sodium lactate, tipranavir, and tromethamine.
19. Recent hospitalization in the last 90 days.
20. Recent infection in the last 90 days requiring prolonged (e.g., >3 weeks) of systemic intravenous antibiotics.
21. Known anemia (HIV+ males Hct< 34; females Hct< 32) or contraindication to donating blood.
22. Poorly controlled hypertension or systolic blood pressure > 140 on repeat measurement in the last 3 months, on more than one occasion.
23. Significant myocardial disease (e.g., current myocarditis or reduced left ventricular ejection fraction below the lower limit of normal) or diagnosed coronary artery disease.
24. History of cardiac arrhythmia that needs to be medically treated.

25. History of psychotic symptoms (e.g., hallucinations, delusional thinking) in the prior 3 months.

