26. History of seizures, abnormal electroencephalogram or brain damage with significant persisting neurological deficit in the past 3 months or currently on anti-seizure medications
27. Significant respiratory disease requiring oxygen.
28. Exposure to any immunomodulatory drug (including maraviroc) in the 12 weeks prior to study.
29. Prior or current use of experimental agents used with the intent to perturb the HIV-1 viral reservoir in the 12 weeks prior to study.
30. Pregnancy. A serum pregnancy test will be performed. If this test is positive, the participant will not be allowed to enter the study since body changes occurring during pregnancy will alter the study results.
31. Recent vaccination within the last 2 weeks prior to study baseline visit. Routine or standard of care vaccinations (such as SARS-CoV-2, influenza, pneumococcal, and meningococcal vaccinations) are allowed but must be administered greater than 14 days prior to baseline study visit. For SARS-CoV-2 vaccination, the last dose must be administered at least 14 days prior to baseline study visit.

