7.1 Allowed Medications and Treatments

Participants may not have exposure to any immunomodulatory drug (including maraviroc) in the 16 weeks prior to study or during study period and may not currently be taking experimental latent HIV reversing agents.

Only concomitant medications that are medically necessary will be continued with appropriate monitoring. In addition, the following medications are prohibited during the study and administration will be considered a protocol violation.

Strict criteria for potential medications that could interact with the study drug will be used, and the following medications are not allowed during the study because of potential interactions with the study medication: acebromphyline, iobenguane, isocarboxazid, methylene blue, moclobemide, phenylzine, procarbazine, rasagiline, safinamide, selegiline, tranylcypromine, asunaprevir, bupropion, topical cocaine, fluoxetine, iohexol, linezolid, paroxetine, potassium citrate, quinidine, sodium bicarbonate, sodium citrate, sodium lactate, tipranavir, and tromethamine. This is because the study medication may alter metabolism of the drugs.

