8 STUDY TREATMENTS

8.1 Method of Assigning Participants to Treatment Groups

Participants will be randomized to either oral methamphetamine versus placebo treatment first using a random number generator. Whichever treatment the participant receives first, they will receive the other treatment (placebo or oral methamphetamine) for their second treatment phase starting at Day 77 (See Study Events Table in Other Documents).

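### The 14-day vaccination exclusion is counted from the baseline visit and not from the two treatment days, so a vaccine given between baseline and dosing, or before the Day 2/78 sample, breaks no stated rule

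*Combined protocol and SAP*

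**What the plan says.** Section 6.3 item 31, repeated as synopsis item 22, excludes "Recent vaccination within the last 2 weeks prior to study baseline visit". Routine vaccines, with influenza and SARS-CoV-2 among those named, "are allowed but must be administered greater than 14 days prior to baseline study visit". Neither item mentions a treatment day or the second phase.

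Section 8.1 has participants cross to the other treatment "for their second treatment phase starting at Day 77". Section 6.2 item 9 asks participants to "maintain the inclusion/exclusion criteria" for the 146 days of the study. The list of prohibited medications in section 7.1 contains no vaccines. The same section does carry the ban on immunomodulatory drugs forward: it applies "in the 16 weeks prior to study or during study period". (Section 6.3 gives a different number of weeks for that ban, which is a separate matter.)

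For infection, section 6.3 lists "Recent infection in the last 90 days requiring prolonged (e.g., >3 weeks) of systemic intravenous antibiotics" and, as indirect cover for severe illness, "Recent hospitalization in the last 90 days".

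Section 14.3 compares post-drug values with the average of three baseline measures. It has no rule for a vaccination or infection that occurs during the study.

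**The concern.** The sponsor has already decided that a vaccine within 14 days can disturb what this study measures: T-cell activation, cytokines, CD4+ T-cell gene expression and HIV transcription. The rule protects the baseline visit. The measurements that carry the treatment effect are taken on and just after the two treatment days.

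A crossover removes stable differences between people. It does not remove a transient stimulus that falls in one phase only. Such a stimulus enters that participant's within-person comparison in full, and with 10 participants each one is a tenth of the mean. Participation lasts about five months and seasonal vaccines are expressly permitted, so the situation is not far-fetched.

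**Working it through.** **Step 1: does any other text close the gap?**

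- Section 6.2 item 9 (criteria must be maintained): a criterion defined by its distance from the baseline visit is settled at that visit. A later vaccination does not breach it.
- Section 7.1: the immunomodulator ban runs through the study period. The vaccine rule has no such extension, and vaccines are not on the prohibited list.
- Section 9.1.1 (recording): at screening and entry it takes concomitant medications from the previous 30 days and a history that names HIV-1 related vaccines. At later visits it asks only for changes in prescription medications. A routine vaccine given mid-study has no explicit place to be recorded.

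**Step 2: is baseline one visit or one per arm?**

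- For one visit: items 31 and 22 use the singular throughout.
- For one per arm: the synopsis describes screening for each arm. Section 2.1 lists viral load at screening, baseline, Day 2 and Day 31 of each treatment arm. Section 9.1.3 speaks of a first baseline visit (B1).
- Section 9.1.3 also lists B1 apart from Entry (Day 0), so baseline is not simply the dosing day under either reading.
- The Study Events Table that would settle this is not in the text.

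**Step 3: chance that at least one of 10 is affected in Phase 2, single-baseline reading.**

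Assumption, not in the documents: 1 or 2 routine vaccinations per person per year, spread evenly. The window that matters is the protocol's own 14 days before dosing plus about 1 day to the Day 78 sample, so 15 days.

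- One per year: 1 − (1 − 15/365)^10 = 0.34
- Two per year: 1 − (1 − 15/365)^20 = 0.57

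**Step 4: the same, per-arm reading.**

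If the Phase 2 baseline falls g days before dosing (g below 14), the uncovered stretch is g + 1 days. The text does not give g. At the lower limit, g = 0:

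- One per year: 1 − (1 − 1/365)^10 = 0.03
- Two per year: 1 − (1 − 1/365)^20 = 0.05

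The answer therefore lies between these values and those of Step 3. Under either reading, Phase 1 has its own baseline-to-dose gap as well.

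**Step 5: what one or two affected participants could do.**

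First, the plan's own figure. Section 14.5 gives n = 10, SD 0.6 log10, alpha 0.05 and about 80% power for a difference of 0.5 to 0.6 in CA-US RNA. A two-sided paired t test, taking 0.6 as the SD of the difference, gives power 0.803 at 0.6 and 0.651 at 0.5. The figure reproduces at the top of the stated range.

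The documents give no effect of a vaccine on CA-US RNA. Purely to show scale, assume a shift of 0.3 to 1.0 log10 in one phase, and take the comparison as methamphetamine against placebo.

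- Mean difference moves by (number affected × shift)/10: 0.03 to 0.10 for one participant, 0.06 to 0.20 for two.
- Stimulus in the placebo phase, true effect 0.6 (simulated): power falls from 0.80 to between 0.76 and 0.55 for one participant, and to between 0.70 and 0.31 for two.
- Stimulus in the methamphetamine phase, no true effect (simulated): the chance of a falsely significant increase rises from 0.025 to between 0.033 and 0.044 for one, and to between 0.043 and 0.080 for two.

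**The case against.** The strongest reply is that baseline may well be per arm. Sections 2.1 and 9.1.3 and the synopsis all point that way. If so, a vaccine on, say, Day 70 could already be barred, depending on when the Phase 2 baseline falls. This stands as a limit on size. It does not close the gap, because the rule still stops at a baseline visit listed separately from Day 0.

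Second, treatment order is randomised, so affected phases fall on drug or placebo by chance. This also stands. A reader might infer that the result is biased towards or away from a drug effect. The design does not support that; in expectation the events add noise and chance imbalance.

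Third, the effect may be small. Activation markers and cytokines are first tested with a Wilcoxon signed rank test, where one extreme value counts only by its rank. If the three baseline measures are taken in each phase, a stimulus that precedes them is partly subtracted out. Both points are fair, but a vaccine given after baseline is not subtracted.

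Fourth, on infection, a reader might infer that acute illness goes unnoticed. It does not: adverse events are sought at every visit with start and stop dates (sections 9.1.7 and 10.1), and treatment days include a targeted examination and temperature (9.1.4, 9.1.5). It is true that no criterion covers an ordinary acute illness near dosing. Adding one would be a new exclusion and not an extension of the protocol's own window.

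**Conclusion.** The vaccination rule protects the wrong date for its purpose. As written, a routine vaccination between baseline and a treatment day, or between dosing and the Day 2/78 sample, is permitted. That rests on the text and needs no assumption.

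The size is conditional. The 34% to 57% chance of at least one affected participant in Phase 2 holds only if baseline is a single visit before Day 0 and if people receive one to two evenly spread vaccinations a year. Under a per-arm baseline the chance is lower, and the documents do not give the interval needed to state it.

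It would go too far to say that Phase 2 is certainly unprotected, or that a vaccine would create or hide a drug effect. The meaning of baseline is unresolved, and no effect size is given. The power and error ranges above depend on an assumed shift and show only that a 10-person study has little margin. This is a real gap in a stated rule that a wording change can close, not a fatal flaw.

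**What to change.** - In section 6.3 item 31 and synopsis item 22, keep the existing 14-day window but count it back from the treatment day of each phase, and run it through that phase's next sample. For example: *no vaccination in the 14 days before the treatment day of either phase, or between that day and the Day 2 (Phase 1) or Day 78 (Phase 2) sample.*
- State whether the baseline visit is one visit or one per arm, and reconcile items 31 and 22 with the synopsis, sections 2.1 and 9.1.3, and the Study Events Table.
- Extend section 9.1.1 to record the date of any vaccination during the study.
- Add to section 14.3 a sensitivity analysis that drops or flags phases with a vaccination, or an acute infection recorded as an adverse event, in the 14 days before dosing or before the post-dose sample.
- Whether to add an acute-infection exclusion is left to the sponsor.

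Cost: a wording amendment, one more recorded date and one more analysis. A visit will occasionally shift. Because screening for each arm is limited to 14 days before treatment, a shift can let it lapse and require repeat screening, with extra blood against the 795 mL total in section 2.1 and extra time against the 146 days.

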7 CONCURRENT MEDICATIONS

Participants may continue to take their usual medications, as long as they are medically necessary and can be monitored during the study period.

7.1 Allowed Medications and Treatments

Participants may not have exposure to any immunomodulatory drug (including maraviroc) in the 16 weeks prior to study or during study period and may not currently be taking experimental latent HIV reversing agents.

Only concomitant medications that are medically necessary will be continued with appropriate monitoring. In addition, the following medications are prohibited during the study and administration will be considered a protocol violation.

Strict criteria for potential medications that could interact with the study drug will be used, and the following medications are not allowed during the study because of potential interactions with the study medication: acebromphyline, iobenguane, isocarboxazid, methylene blue, moclobemide, phenylzine, procarbazine, rasagiline, safinamide, selegiline, tranylcypromine, asunaprevir, bupropion, topical cocaine, fluoxetine, iohexol, linezolid, paroxetine, potassium citrate, quinidine, sodium bicarbonate, sodium citrate, sodium lactate, tipranavir, and tromethamine. This is because the study medication may alter metabolism of the drugs.

8 STUDY TREATMENTS

8.1 Method of Assigning Participants to Treatment Groups

Participants will be randomized to either oral methamphetamine versus placebo treatment first using a random number generator. Whichever treatment the participant receives first, they will receive the other treatment (placebo or oral methamphetamine) for their second treatment phase starting at Day 77 (See Study Events Table in Other Documents).

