4 STUDY DESIGN

4.1 Study Overview

This is a phase IV open label randomized, double-blinded, placebo-controlled crossover study. A placebo treatment arm will be assigned to participants in a randomized crossover design. HIV+ ART-suppressed individuals with no prior history of MA use disorder will be administered 10mg oral methamphetamine hydrochloride (Desoxyn®), followed by 15 mg methamphetamine hydrochloride two hours later, for a total of 25mg in one 24-hour period (the maximum FDA approved daily dose for the treatment of childhood obesity). Participants will complete the study twice (once on a placebo treatment arm and once with the Desoxyn® treatment arm). Which treatment arm occurs first will be randomly assigned and will include a 31-day washout period between the two phases. The placebo is similar in appearance, consistency, and taste to methamphetamine hydrochloride tablets, USP (Desoxyn®), without any known drug-drug interactions (e.g., changes in pH balance that might affect drug absorption) with HIV antiretroviral therapy.

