8.2 Blinding

The order in which participants complete the two treatment phases (i.e., oral methamphetamine and placebo) will be unknown to both the participants and the PI/study team. Both the oral methamphetamine and placebo will be prepared in identical capsules by the UCSF CTSI investigational pharmacist, out of sight of the study participant, study coordinator, and study site PI and administered to the participant to maintain double blinding. The investigational pharmacist will randomize each participant according to the methods described above. In the event that participant experiences an adverse event that requires the identity of the study drug be revealed, the PI will be able to contact the investigational pharmacist to break the blind. In the event that a participant blind is broken, the study PIs will determine the impact upon the un-blinded participant's continued participation in the study and if a replacement participant is needed on a case-by-case basis.

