14.3 Analysis of Primary Endpoint

Paired analyses using Wilcoxon signed rank tests will be performed to evaluate whether there is a statistically significant change in markers of immune activation (e.g., CD69, CD38, and/or HLA-DR) on CD4+ and CD8+ T cells, as well as log-transformed levels of plasma cytokines (e.g., IL-6, IL-1b, IFN- γ) after study drug compared to baseline (reference will be the average of the three baseline measures). Multivariate analyses will then be performed to evaluate the association between study drug and measures of immune activation at post-dosing, using linear mixed effects models, which account for within-participant correlation of observations and allows for greater stability in the estimate of the outcome measures within individuals. Similarly, for measures of the HIV transcription, linear mixed effects regression to compare CA-US RNA levels before and after study drug will be performed. Negative binomial mixed effects regression (a method to analyze over-dispersed count data) to compare plasma HIV RNA levels before and after study drug administration (reference will be the average of three baseline measures).

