14.5 Sample Size

Assuming a log normal distribution of HIV-1 cell-associated (CA)-US RNA and a standard deviation of 0.6 log₁₀ copies/10⁶ CD4+ T cells (as above for Aim 1125), with 10 participants in the treatment arm, and a null hypothesis of no change in CA-US RNA, we estimate that the study will have approximately 80% power to detect a 0.5-0.6 log₁₀ difference in CA-US RNA before and after treatment peak, at the 0.05 significance level. For the gene expression analyses, assuming a coefficient of variation of 0.32 and approximately 80-90% sequencing depth between 5 to 8 copies per base, respectively, we estimate having greater than 80% power to detect a two-fold change at the 0.05 significance level.

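### Treatment order for 10 participants is randomised with no stated restriction on the sequence split, and no planned model has a period term

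*Combined protocol and SAP*

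**What the plan says.** The design is a two-period placebo-controlled crossover. Section 4.1 states: "Which treatment arm occurs first will be randomly assigned and will include a 31-day washout period between the two phases". Section 8.1 describes allocation in one sentence, "Participants will be randomized to either oral methamphetamine versus placebo treatment first using a random number generator", and has each participant cross over "for their second treatment phase starting at Day 77". Section 8.2 adds: "The investigational pharmacist will randomize each participant according to the methods described above". Neither section mentions blocks, a pre-generated list or a target number per sequence, and neither rules them out.

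For cell-associated unspliced HIV RNA (CA-US RNA), Section 14.3 says "linear mixed effects regression to compare CA-US RNA levels before and after study drug will be performed". The covariates in Section 14.4 are demographic, immunological, treatment-history and drug-use variables; period and sequence are not among them. No MA-minus-placebo contrast is written down. Section 14.5 sizes the trial as a one-group comparison, "with 10 participants in the treatment arm, and a null hypothesis of no change in CA-US RNA", and does not consider the sequence split.

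Section 12.4 replaces participants who withdraw before their last dosing day, and Section 8.2 allows replacement case by case after a broken blind. Neither says which sequence the replacement receives.

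**The concern.** In a two-sequence crossover, the MA-placebo contrast is protected against differences between periods in one of two ways: equal numbers in each sequence, or a period term in the model. The plan secures neither. With 10 participants, unrestricted allocation can leave sequences of 7 and 3 or 8 and 2, and a split once obtained cannot be rebalanced.

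What is at stake depends on the model. With period included, imbalance costs precision. With period left out, imbalance lets part of any period effect into the estimated drug effect. The power in Section 14.5 is only about 80% for the stated target, so there is little slack.

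**Working it through.** **Inputs.** N = 10, SD 0.6 log10, target 0.5 to 0.6 log10, power about 80% and alpha 0.05 come from Section 14.5. Four assumptions are added because the documents are silent: alpha is two-sided; 0.6 is the SD of the within-person difference, used for both the before-after change and the MA-placebo difference; allocation is 1:1 and independent for each participant; the period effect is 0.1, 0.2 or 0.3 log10.

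**1. The plan's own figure.** Section 14.5 says: "we estimate that the study will have approximately 80% power to detect a 0.5-0.6" log10. The smallest difference detectable with 80% power is:
- Normal approximation: 0.6 × (1.960 + 0.842)/√10 = 0.532.
- Noncentral t, 9 df: 0.598.

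The stated range is reproduced. On the t basis, power is 80.3% at 0.6 and 65.1% at 0.5, so 80% is reached only at the upper end.

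**2. Chance of each split.** Under Binomial(10, 0.5):
- 5:5 is 252/1024 = 24.6%.
- 6:4 is 420/1024 = 41.0%.
- 7:3 or worse is 2 × (1 + 10 + 45 + 120)/1024 = 352/1024 = 34.4%.
- 8:2 or worse is 112/1024 = 10.9%.

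**3. Period term in the model.** The estimate is half the sum of the two sequence means, suitably signed. Its SE is (0.6/2) × √(1/n1 + 1/n2), with 8 df. The variance relative to 5:5 is (1/n1 + 1/n2)/0.4; at 7:3, for example, 0.476/0.4 = 1.19.

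| Split | Variance ratio | SE | Detectable at 80% power | Power at 0.6 |
|---|---|---|---|---|
| 5:5 | 1.00 | 0.190 | 0.607 | 79.1% |
| 6:4 | 1.04 | 0.194 | 0.620 | 77.4% |
| 7:3 | 1.19 | 0.207 | 0.663 | 71.9% |
| 8:2 | 1.56 | 0.237 | 0.759 | 60.3% |

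Averaged over all splits under independent allocation (10:0 counted as zero power), power at 0.6 is 74.1%. Forcing 5:5 recovers 79.1 − 74.1 = 5.0 points.

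**4. No period term.** Let p be the period 2 minus period 1 difference in the analysed outcome. The within-person MA-minus-placebo difference is shifted by +p in the placebo-first sequence and by −p in the MA-first sequence. The mean is therefore shifted by p × (n1 − n2)/10, where n1 is the number given placebo first. That is 20% of p at 6:4, 40% at 7:3 and 60% at 8:2. Type I error given the split was simulated with 100,000 runs per case:

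| Assumed p (log10) | Shift at 7:3 | Shift at 8:2 | Type I error at 5:5 | At 7:3 | At 8:2 |
|---|---|---|---|---|---|
| 0.1 | 0.04 | 0.06 | 4.7% | 5.2% | 5.8% |
| 0.2 | 0.08 | 0.12 | 3.9% | 5.5% | 7.6% |
| 0.3 | 0.12 | 0.18 | 3.1% | 6.0% | 10.5% |

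**5. Sensitivity to the SD.** If 0.6 is instead a between-person SD, the detectable difference in step 1 (t) is 0.71 at a within-person correlation of 0.3 and 0.46 at 0.7. The variance ratios and bias shares do not depend on the SD.

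**The case against.** Four stronger readings are tempting, and the documents support none of them.

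- **That simple randomisation was chosen.** A random number generator can produce permuted blocks as easily as independent draws, and the wording in Section 8.2 fits either. What is established is that no restriction is specified, so unrestricted allocation would comply with the protocol.
- **That a lopsided split is likely.** Some departure from 5:5 has probability 75%, but more than half of that is 6:4, at a 4% cost in variance. A split that matters is about a one-in-three event.
- **That the trial loses precision and is also biased.** These are alternatives. A period term removes the bias and makes imbalance cost variance. Without it, the sampling variance of the paired mean does not depend on the split, so the 19% and 56% figures do not apply.
- **That eleven weeks of drift (Day 77) passes straight into the drug effect.** The synopsis describes screening for each arm, and Section 2.1 lists viral load at screening and baseline and on two later days of each arm. If baselines are taken within each period, a shift common to baseline and post-dose values cancels. Section 9.3.2 uses cryopreserved cells, so batch differences between periods are not inherent.

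The bias also averages to zero over repeated randomisations, and the documents give no size for a period effect. These points limit the concern but do not dispose of it. The trial is run once, so the realised split is what counts. Section 14.3 does not say whether its averaged baseline is specific to each period, and a period effect on the acute response would survive baseline subtraction. The Wilcoxon signed-rank tests listed there have no period term, so using them for the MA-placebo contrast would rely on balance by design.

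**Conclusion.** The point holds as a gap worth closing before randomisation starts. Given independent 1:1 allocation, about one trial in three would end 7:3 or worse and one in nine 8:2 or worse. With a period term the average cost is about 5 points of power at 0.6 log10, and about 19 points (79.1% to 60.3%) at 8:2. Without one, 40% or 60% of the period effect left after any baseline correction enters the MA-placebo estimate. For an assumed 0.2 log10 that is 0.08 or 0.12 log10, against a target of 0.5 to 0.6.

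The split probabilities rest on the unstated allocation rule, the power figures on the reading of 0.6, and the bias on an assumed period effect. All of it concerns the contrast that the crossover design implies, which Section 14.3 does not yet define.

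**What to change.** - **Section 8.1:** state that the investigational pharmacist uses a pre-generated, concealed list balanced 5:5 across the two sequences. Blocks of 4 would be a weaker alternative: with 10 participants the worst result is 6:4, with probability 1/3.
- **Sections 8.2 and 12.4:** have the pharmacist assign replacements from a concealed reserve list built to keep the balance. A replacement should not automatically inherit the sequence when the replaced participant's blind was broken, because the PI would then know the new allocation. If one such replacement tips completers to 6:4, the variance cost is 4%.
- **Sections 14.3 and 14.4:** define the MA-versus-placebo contrast, say whether the baseline is specific to each period, and add period and sequence as fixed effects in the mixed models.

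The cost is a few sentences and one or two degrees of freedom (8 rather than 9 for the paired contrast). No clinical procedure changes. The drawback is that, with a known 5:5 total, the last allocations become more predictable if earlier ones are guessed. Guessing is plausible because Section 2.1 lists raised blood pressure and heart rate as likely effects, so the list should stay with the pharmacist.
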